1.2. Aim of the study

The overall aim of this study is to develop and test a prognostic tool for knee pain in children and adolescents to be used in general practice.

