1.4. Specific objectives of the study

- 1) Identification of prognostic factors for knee pain in children and adolescents**
 - a) Review of prognostic factors for knee pain in children and adolescents from current literature**
 - b) Selection of prognostic factors to be included in the prognostic tool**
- 2) Development of a prognostic model**
 - a) Development of the questions to be included in the prognostic tool**
 - b) Discussion about the questions wording with GPs**
 - c) Identification of the most suitable form to deliver the prognostic tool**
- 3) Piloting the prognostic tool and recruitment procedures**
 - a) Testing the prognostic tool at the general practices**
 - i) Assess time taken to use the prognostic tool**

- ii) Assess quality/acceptability of the prognostic tool (e.g. content of the questions and domains included, acceptability and understanding of the questions used, acceptability of the delivery of the tool, face validity, construct validity, criterion validity)
- b) Assess participants' recruitment processes
 - i) Assess baseline response (e.g. ratio between children who participated in the study over all those who consulted for knee pain as recorded with codes for consultation) and reasons for non-participation
 - c) Improvement of the prognostic tool and of the recruitment procedures
- 4) Recruitment of children and adolescents and collection and analysis of the data
 - a) Description of the sample characteristics
 - b) Assess the predictive ability of the prognostic tool
 - i) Sensitivity
 - ii) Specificity
 - c) Assess baseline response and reasons for non-participation
 - d) Assess loss to follow-up and reasons for dropping out of the study where possible
- 5) Cost-effectiveness of the study (optional depending on time availability)
 - a) Assess the workload for GPs, researchers and administrative staff
 - b) Assess the time needed to deliver the tool in general practice and identification of alternative solutions to deliver the tool (e.g. by using iPads etc)
 - c) Assess satisfaction of the participants and general practitioners with the study
 - d) Evaluation of the effectiveness and suitability of this study in light of the resources available in general practice

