1.5. Study design

Prospective cohort study. Data will be collected at baseline through a questionnaire delivered at the general practice if the primary recruitment strategy will be applied. Otherwise, the baseline collection of the data will occur through a questionnaire home-mailed or delivered through a survey internet link if a strategy of recruitment through social media will be applied (please see section 2.7.2 for a description of the recruitment strategies). Outcomes will be collected by questionnaires either self-reported or parent-reported (collected through e-mail or text messages) at follow-up.

2. Methods

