month period (which is the duration of the baseline recruitment). If 30% of these children decide to take part in the study, there will be data on 300 children aged 8-19 at baseline. However, for the development of the START-BACK screening tool 244 patients were identified, of which only 131 (54%) returned the baseline questionnaire and 107 (82%) agreed to further contact ²⁹. Therefore, if we aimed at only 100 children aged 8-19 years old with a consultation for knee pain in a 6-month period and by keeping the same proportions shown above (i.e. only 30% baseline participation rate), only 56 general practices of a medium size of 5000 individuals each would be needed (corresponding to a target population of 280.000 individuals, of which 56.000 aged 8-19 years old). A target of 100 children would enable approximately 30 individuals in each prognostic risk group (low/medium/high).

Conversely, based on the highest prevalence estimate (200 per 10,000 registered persons) and considering a 30% participation rate into the study, 33 general practices of a medium size of 5000 individuals each would be needed (corresponding to a target population of 165.000 individuals, of which 33.000 aged 8-19 years old) to recruit at least 100 children. To recruit at least 300 children, 100 general practices of a medium size of 5000 individuals each would be needed (corresponding to a target population of 500.000 individuals, of which 100.000 aged 8-19 years old). Alternatively, it might be possible to target fewer bigger general practices (e.g. 18 general practices of a medium size of 10.000 individuals to recruit 100 children).

In addition, if only 100 children will be recruited from general practices, it might be possible to perform an extra recruitment through social media that would complement the group of children recruited through general practices, in order to achieve a total sample size of at least 300 children. In this case, sensitivity analysis would be performed to check for any potential difference in characteristics between the sample recruited through general practices and social media.

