2.10. Analysis plan

The analysis plan that will lead to the development of the final prognostic tool will include the following stages:

1. Descriptive analysis of the collected data. Results will be presented as means with SDs and as percentages.
2. Assessment of potential floor and ceiling effects of the items included in the prognostic tool. This will be done by checking that for those items that represent an ordinal or categorical variable with more than two potential response categories, the responses given are not skewed towards the top or bottom extreme of the scales (e.g. a ceiling or floor effect is present if >15% of the respondents report the lowest/highest score of the scale ^{42,45,57}).
3. Estimation of knee pain prognosis (i.e. recurrence/persistence of knee pain, dichotomous outcome) at 3-month and 6-month follow-up by means of multiple logistic regression to estimate ORs and 95% confidence intervals for each item included in the tool. This will inform on which factors are most related to the prognosis of knee pain and will provide an insight on the scores of the prognostic tool (both overall and for subscales) to be applied for the creation of the initial risk groups. Alternatively, the RR will be estimated if a general linear model analysis will be carried out.
4. Discriminant validity of the prognostic score will be assessed by using receiver operating characteristics (ROC) curves and by calculating the area under the curve (AUC) for the overall score and subscales of the prognostic tool.

[figure not shown]
5. Creation of risk groups for the recurrence/persistence of knee pain on the basis of cut-off scores identified using the ROC curves for the overall tool score. The initial idea is to have three risk groups (low/medium/high), which have to be clinically meaningful. More importance will be given to the sensitivity of the tool over the specificity.
6. Assessment of the predictive ability of the risk groups defined at baseline by calculating the sensitivity, specificity and negative and positive likelihood ratios (LRs) against the primary and secondary outcome (i.e. 3-month and 6-month recurrence/persistence of knee pain; disability/activities limitation due to knee pain).
7. Assessment of the potential influence of non-modifiable patients' characteristics on the predictive ability of the risk groups defined at baseline by stratifying the former analysis by age groups and sex.

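### The tool's score, cut-offs and reported accuracy all come from the same children, with no correction for optimism

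*Combined protocol and SAP*

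**What the plan says.** Section 1.2 sets out to "develop and test a prognostic tool for knee pain in children and adolescents", and section 1.5 describes one design: "Prospective cohort study. Data will be collected at baseline through a questionnaire delivered at the general practice". Objective 4b in section 1.4 is to "Assess the predictive ability of the prognostic tool", listing sensitivity and specificity.

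Section 2.10 then gives one sequence of steps:

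- Step 3 fits a multiple logistic regression to show "which factors are most related to the prognosis of knee pain and will provide an insight on the scores of the prognostic tool", from which the initial risk groups are to be built.
- Step 4 calculates the ROC curve and AUC of the score.
- Step 5 forms the risk groups, provisionally three, "on the basis of cut-off scores identified using the ROC curves for the overall tool score", and adds: "More importance will be given to the sensitivity of the tool over the specificity".
- Step 6 is "Assessment of the predictive ability of the risk groups defined at baseline by calculating the sensitivity, specificity", together with positive and negative likelihood ratios.

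No step names a second data set, and no step states how the regression results become scores.

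**The concern.** A score tuned to a sample, and a cut-off chosen on that sample's ROC curve, fit the chance features of that sample as well as the real signal. Accuracy measured on the same children is therefore expected to exceed accuracy in the next children seen. Sensitivity and specificity are a stated objective, and step 5 puts sensitivity first, so the figure readers will rely on most is affected. Section 1.1 itself warns that children wrongly classed as low-risk may be undertreated, and overstated sensitivity hides exactly that error.

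The size of the problem depends on the scoring rule, which the text leaves open. Three readings fit it:

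- (a) weights taken from the regression;
- (b) items selected by the regression, then summed without weights;
- (c) an unweighted sum fixed in advance.

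**Working it through.** **Is the gap filled elsewhere?** No.

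- The validity named in sections 1.4 and 2.8.6 is face, content, construct or criterion validity at the pilot stage.
- Section 2.8.7 is test-retest stability.
- Section 2.5 compares the characteristics of the two recruitment sources.
- Section 2.11 compares complete-case with imputed results.
- Step 7 of section 2.10 stratifies the same results by age and sex.

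A figure in section 2.10 and Figure 4 could not be seen, but the surrounding text gives no sign that they describe validation.

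**The plan's sample size.** Section 2.5 reproduces: 168 × 5,000 × 0.20 × 119/10,000 × 0.5 × 0.30 = 299.9, stated as 300. If recruitment at practices stops at 100, an optional social-media top-up is foreseen "in order to achieve a total sample size of at least 300 children".

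**Number of terms (from the questionnaire in section 2.6).** There are 13 numbered questions, and questions 9 and 10 each hold two items, giving 15 items. One linear term each gives 15 terms. Dummy coding of the multi-category items gives 39.

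**Event rate.** The documents give none at 3 months. Section 1.1 reports about 50% of adolescents still having knee pain at 1 or 2 years, so 50% is assumed, with 30% and 70% also run. At 50%, 300 children give 150 events: 150/15 = 10 per term, or 150/39 = 3.8. With 100 children it is 50/15 = 3.3.

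**Main simulation.** It used 15 terms with the questionnaire's category counts, a latent inter-item correlation of 0.15, 10 truly prognostic items, a maximum-likelihood logistic fit, and testing on 20,000 new subjects per replicate (400 to 500 replicates). Optimism = apparent value − value in new subjects. Pairs are for a best attainable AUC of 0.70 / 0.75. The sensitivity column uses a cut-off targeting 80%.

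| Scoring rule | n | AUC, apparent vs new | Sensitivity, apparent vs new |
|---|---|---|---|
| (a) fitted weights | 300 | 0.732 vs 0.669 / 0.775 vs 0.724 | 0.803 vs 0.751 / 0.803 vs 0.757 |
| (b) selected, unweighted | 300 | gap 0.048 to 0.059 | gap 4.0 to 4.6 points |
| (c) pre-set sum | 300 | 0.675 vs 0.676 / 0.718 vs 0.721 | gap 0.5 / 0.4 points |
| (a) fitted weights | 100 | 0.793 vs 0.630 / 0.826 vs 0.685 | 0.808 vs 0.669 / 0.808 vs 0.681 |
| (b) selected, unweighted | 100 | gap 0.116 to 0.144 | gap 9.2 to 11.5 points |
| (c) pre-set sum | 100 | gap about 0 | gap about 1.5 to 2 points |

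Under (a) at n = 300:

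- AUC optimism is 0.732 − 0.669 = 0.063 and 0.775 − 0.724 = 0.051. The apparent AUC exceeded the new-subject AUC in 96 to 99% of simulated studies.
- Missed cases rise from about 20 per 100 to (1 − 0.757) × 100 = 24.3 and (1 − 0.751) × 100 = 24.9.
- The negative likelihood ratio is reported as 0.33 to 0.38 where new children would give 0.44 to 0.52.
- The median calibration slope in new subjects is 0.67 / 0.74.

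**Other event rates, (a), n = 300.** At 30% events, AUC optimism is 0.075 / 0.061 and sensitivity is overstated by 8.0 / 7.3 points. At 70% it is 0.073 / 0.060 and 3.5 / 3.2 points, with specificity overstated by 7.1 / 6.6 points.

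**Second simulation, different predictors.** With independent normal predictors and 1,000 samples per scenario (n = 300, 15 terms, attainable AUC 0.70), the AUC is 0.732 vs 0.665. At a cut-off holding sensitivity at 0.80 or more, sensitivity is 0.81 vs 0.75 and specificity 0.51 vs 0.46. The negative likelihood ratio is then (1 − 0.81)/0.51 = 0.37 vs (1 − 0.75)/0.46 = 0.54, close to the main result. At attainable AUC 0.65, the AUC is 0.694 vs 0.618. With 39 terms, AUC optimism rises to between 0.819 − 0.697 = 0.122 and 0.753 − 0.584 = 0.169.

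**The case against.** The best defence is that the text never commits to regression weights. Section 2.6 says items were chosen beforehand from literature, individual-participant meta-analysis and discussion with practitioners, and it presents the form as final. Step 3 estimates an odds ratio per item and states no selection rule. If the score is a pre-set sum, the AUC is not optimistic and sensitivity is overstated by only about half a point at n = 300 with an 80% target. That stands, and it is why the conclusion is conditional. But section 2.10 opens by saying that the analysis leads to the final tool, step 3 ties the regression to the scores, and items such as knee side and sex have no natural place in a plain sum. Readings (a) and (b) therefore remain open.

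The figures are also less firm than their decimals suggest. They rest on an assumed event rate and term count, and on a single cut-off where step 5 intends three groups that must also make clinical sense. A Youden cut-off shows larger sensitivity gaps (about 6.5 to 7 points under (a) at n = 300), but it weighs sensitivity and specificity equally, contrary to step 5, so it is not relied on here. None of this changes the direction of the error. More terms or fewer events per term make it larger.

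**Conclusion.** The concern holds. As written, the plan would meet objective 4b with apparent values only, and these are expected to be too high on average unless the score is fixed in advance. At n = 300 with 15 linear terms, 50% events and attainable AUC 0.70 to 0.75, AUC is overstated by about 0.05 to 0.06 and sensitivity at the 80% target by about 4 to 5 points under (a) or (b).

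Across event rates of 30 to 70% under (a), a reported 20 misses per 100 becomes roughly 23 to 28. Under (c) it is about 20.5. If only about 100 children are analysed without the top-up, fitted weights overstate AUC by about 0.14 to 0.16 and sensitivity by 13 to 14 points at the 80% target. These are averages; a single study may fall either side, though rarely on the favourable side when weights are fitted at n = 300. The point should be settled before the data are analysed.

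**What to change.** In section 2.10:

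1. State the scoring rule and the cut-off rule in advance, keeping the priority for sensitivity that step 5 already gives.
2. Repeat every data-driven step (imputation, item selection, weighting and cut-off choice) in bootstrap samples, for example 500. Report optimism-corrected AUC, sensitivity, specificity, likelihood ratios and calibration slope beside the apparent values.
3. If weights are fitted, shrink them or use penalised regression.
4. If a pre-set unweighted sum is chosen, say so; then mainly the cut-off step needs correcting.
5. Describe the results as internally validated development performance. If no correction is made, label them as apparent performance.

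The cost is SAP wording and an estimated few days of analyst time, with no new data, and less favourable published figures. The bootstrap does not remove all bias. In a check with 80 resamples and no imputation, corrected versus new-subject AUC at n = 300 was 0.678 vs 0.668 and 0.731 vs 0.723, with under 1 point of sensitivity left at the 80% target. At n = 100 it left about 0.03 to 0.04 of AUC and 2 to 3 points of sensitivity, which should be stated if that size is analysed.

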1.1. Background and rationale for the study

Knee pain is experienced by 33% of adolescents¹, and the prognosis of knee pain is often unfavorable, with approximately 50% of adolescents still reporting knee pain after 1 or 2 years^{1,2}. Common child and adolescent knee pain includes a variety of conditions (e.g. patellofemoral pain, patella tendinopathy, fat pad impingement, Osgood-Schlatter and Sinding-Larsen-Johansson disease), with specific treatments provided (e.g. education, activity modification, flexibility and strengthening exercises, cryotherapy, orthoses, patellar taping, medications) depending on the condition^{3,4}. Knee pain is linked to both health and social consequences³. Children and adolescents with knee pain are more likely to reduce their sport participation, with following issues regarding the overall health (e.g. poor cardiovascular health, higher adiposity, impaired sleep)^{1,5-8}, to have a higher rate of school absence^{6,9} and to be affected in the choice and performance of future work activities^{10,11}. Knee pain in children and adolescents has also an economic impact, which include both direct (e.g. primary care visits, community services use, medication use) and indirect (e.g. parental productivity work loss and days off work) costs^{12,13}. Knee pain in childhood and adolescence may also persist in adulthood; previous studies have shown that a high proportion of them experience recurrence of symptoms over up to 20 years of follow-up^{14,15}, and adolescent knee pain might be a precursor of adult knee conditions such as knee osteoarthritis¹⁶⁻¹⁹. While there is a body of research on adult knee pain²⁰⁻²², less is known in children and adolescents, who are a distinct population compared to adults with different physiology and psychosocial development^{5,23}. Potential prognostic factors for knee pain identified in previous studies conducted in adolescents include female gender, high leisure time sport

participation, low health-related quality of life, high baseline frequency of knee pain ². A proportion of children and adolescents with knee pain will consult the general practitioner because of their condition; previous research has shown an annual consultation prevalence for knee pain in children and adolescents of 119 ²⁴ - 200 ²⁵ per 10,000 registered persons.

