2.6. Development of the tool

Clinically meaningful prognostic factors for knee pain in children and adolescents were identified from a review of the current literature on the topic. Initially, the most important domains for the prognosis of knee pain and the specific items to be included in the tool were selected based on the strength of association from previous studies identified within the literature and from meta-analysis of individual participant data. Additional factors were included after discussion with general practitioners that agreed to take part to the study and staff working at the Center for General Practice at Aalborg University. During this stage, great emphasis was given to include only the most necessary factors taking in mind that the prognostic tool should be used in a reasonable time of a consultation within general practice.

Items relative to the specific prognostic factors were initially selected from validated scales where possible (e.g. regarding pain characteristics, limitation in daily activities, sport participation, psychological factors). When multiple items within a scale or multiple scales were available for a prognostic factor, the relevant literature on the topic was identified and discussed at meetings with general practitioners and staff working at the Center of General Practice at Aalborg University in order to select the most appropriate items within the possible options. Following previous tools developed for pain in children and adolescents^{28,48,49}, items were properly worded for the age and properly framed with respect to the response options (e.g. direction, time intervals, avoiding double-barreled items).

The initial version of the tool was tested and implemented during the pilot stage (great emphasis was given to the cognitive interviews that were carried out with children and adolescents), until reaching a final version that will be used for the collection of the data, as further described below in section 2.8.6. The outline of the final tool is provided in the figure below:

Knæ project

Disse spørgsmål handler om dine knæsmerter. Sæt kryds i den boks som bedst beskriver hvordan du har det, eller skriv i tekstdokumentet. Hvis du er i tvivl, så bedes du svare så godt du kan. Spørgsmålene står i venstre side, og svarmulighederne i højre side af skemaet.

Navn	
1. Hvor gammel er du?	(_____)
2. Er du en pige eller en dreng?	 Pige  Dreng

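### Step 7 looks for an influence of age and sex only through sensitivity, specificity and likelihood ratios at a common cut-off, so if either item is scored it cannot separate an expected threshold shift from a true difference in performance

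*Combined protocol and SAP*

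**What the plan says.** The relevant parts of section 2.10 form a chain.

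- Step 3 fits a multiple logistic regression that yields an odds ratio "for each item included in the tool". The results are to inform the scores; no weights are fixed.
- Step 4 plans an AUC for the overall score and subscales, not by age or sex.
- Step 5 forms risk groups from "cut-off scores identified using the ROC curves for the overall tool score", favouring sensitivity over specificity. No stratum-specific cut-off is described.
- Step 6 measures predictive ability by "calculating the sensitivity, specificity and negative and positive likelihood ratios (LRs) against the primary and secondary outcome".
- Step 7 assesses the influence of fixed characteristics on the "predictive ability of the risk groups defined at baseline by stratifying the former analysis by age groups and sex".

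In section 2.6 the final tool opens with "1. Hvor gammel er du" (age) and "2. Er du en pige eller en dreng" (sex). Section 1.1 states: "Potential prognostic factors for knee pain identified in previous studies conducted in adolescents include female gender". It gives no effect size, and age is not in that list. Section 2.10 mentions no calibration measure, stratum-specific AUC or interaction term.

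**The concern.** Sensitivity and specificity at a fixed cut-off depend on where a group's scores lie relative to the cut-off as well as on how well the score ranks children. If being a girl, or being older, adds points, that stratum's scores move up as a block. More of its children with a poor outcome fall above the cut-off, and so do more of its children with a good outcome. Sensitivity rises, specificity falls, and the likelihood ratios move too. The other stratum does the reverse. None of this requires the tool to work better or worse in either stratum.

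Step 7 is meant to find out whether age and sex alter predictive ability. With these metrics alone, a gap between boys and girls could be the built-in shift, a real difference in performance, or both, and the planned output gives no means of telling which.

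**Working it through.** **The plan's own figures.** There is none for step 7. The sample size is needed to gauge noise. Section 2.5 takes 10 per item × 30 items = 300, and 168 practices × 5000 × 20% × 119/10,000 × 1/2 × 30% = 299.9, so the 300 reproduces. The fallback from general practice is 100.

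**Assumed inputs** (not given in the documents):

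- two equal strata by sex;
- 50% event rate (section 1.1 gives about 50% at 1 or 2 years; no 3-month primary-care figure is stated);
- cut-off giving 90% pooled sensitivity (the plan favours sensitivity but sets no target);
- all other items combined as a normal term Z with SD 0.9, which gives an overall AUC of about 0.73;
- one cut-off. The plan envisages three groups; the same reasoning applies at each boundary.

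**Model.** logit(p) = a + b·sex + Z, with b = ln(OR), a solved for 50% events, and no interaction. The score is b·sex + Z, so it is correctly calibrated in both sexes. For cut-off c, within each stratum:

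- sensitivity = E[p·1(score ≥ c)] / E[p]
- specificity = E[(1−p)·1(score < c)] / E[1−p]

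| Sex OR | Higher-scoring sex, sens/spec | Lower-scoring sex, sens/spec | Gap (points, before rounding) | AUC in each sex |
|---|---|---|---|---|
| 1.0 | equal | equal | 0 / 0 | 0.72, 0.72 |
| 1.2 | 0.92 / 0.29 | 0.88 / 0.36 | 3 / 7 | 0.72, 0.72 |
| 1.5 | 0.93 / 0.25 | 0.86 / 0.40 | 7 / 15 | 0.72, 0.72 |
| 2.0 | 0.95 / 0.20 | 0.83 / 0.45 | 12 / 25 | 0.72, 0.72 |

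**Likelihood ratios at OR 2.0.** LR+ = sens/(1−spec): 0.95/0.80 = 1.19 against 0.83/0.55 = 1.51. LR− = (1−sens)/spec: 0.05/0.20 = 0.25 against 0.17/0.45 = 0.38. They shift as well, so they do not rescue the comparison.

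**Age.** With an assumed OR of 1.10 per year, ages 8–13 give 0.84/0.44 and ages 14–19 give 0.94/0.23, with AUC 0.72 in both. That OR amounts to 1.10^6 = 1.77 between bands whose midpoints are six years apart, which is not a small effect.

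**Other operating points.** At 80% pooled sensitivity, with within-stratum AUC 0.68 to 0.80 and 30% to 50% events, the sensitivity/specificity gaps are 3–7 / 4–10 points at OR 1.2, 7–16 / 9–22 at OR 1.5, and 12–26 / 16–36 at OR 2. The largest AUC gap between strata, for ORs up to 3, is 0.006.

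**If sex is prognostic but not scored.** At OR 2.0 and 90% pooled sensitivity, the gaps are about 2 and 4 points, in the opposite direction.

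**Noise.** The 95% half-width of a difference is 1.96·√[(p₁q₁ + p₂q₂)/n], with n = 75 events (or non-events) per stratum at N = 300.

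- OR 1.5, sensitivity: 1.96·√[(0.0651 + 0.1204)/75] = 0.10, against a gap of 0.07.
- OR 1.5, specificity: 1.96·√[(0.1875 + 0.2400)/75] = 0.15, against 0.15.
- OR 2.0, sensitivity: 1.96·√[(0.0475 + 0.1411)/75] = 0.10, against 0.12.
- OR 2.0, specificity: 1.96·√[(0.1600 + 0.2475)/75] = 0.14, against 0.25.

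At N = 100 the half-widths are √3 times larger: about 0.17 and 0.25 at OR 2.0.

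**The case against.** Four points can be made for the plan.

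*Scoring is not stated.* A reader might infer that age and sex are certain to carry points and that large differences must therefore appear. The documents do not support that. Step 3 only informs the scores, no weights exist yet, no odds ratio for sex is given, and age is not among the prognostic factors listed in section 1.1. That they will be scored is a fair inference from step 3 covering every item, and nothing excludes items 1 and 2, but it remains conditional. This stands and limits the point.

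*The stratified figures are real.* A reader might infer that they are meaningless. They are not. If sensitivity is 0.83 in boys and 0.95 in girls, more boys with a poor outcome are in fact placed in the low-risk group, and section 1.1 itself worries about undertreating such patients. The figures describe classification errors correctly; what they cannot do is attribute them to a difference in performance. This stands, and is why they should be kept.

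*No harmful decision follows.* A reader might foresee unneeded sex- or age-specific cut-offs. Step 7 contains no test, decision rule or separate cut-offs, so that is speculation.

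*Noise will dominate.* With 300 children, gaps at OR 1.2 or 1.5 would not clearly exceed sampling error, and with 100 even those at OR 2.0 would not. That reduces the chance of a false finding, but it does not make the metric answer the question asked.

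**Conclusion.** The point holds conditionally. If age or sex receives weight, differences between strata in sensitivity, specificity and likelihood ratios are expected at a common cut-off even with equal AUC and calibration, and step 7 as written cannot distinguish them from a true difference in performance. Under the stated assumptions the size runs from minor (3 and 7 points at OR 1.2) to substantial (12 and 25 points at OR 2.0). It shrinks to about 2 and 4 points, reversed, if sex is prognostic at OR 2.0 but unscored. The direction follows from the design once an item is scored; the size rests on inputs that the documents do not supply. This is an inexpensive improvement to a secondary, descriptive step, and does not affect the main analysis.

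**What to change.** Reword step 7 as follows.

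1. Judge influence on predictive ability by the AUC of the score and the observed 3-month risk per risk group, within each sex and age stratum, with 95% confidence intervals. Show the mean predicted risk for the same children beside each observed risk. Observed risks alone can differ between strata when calibration is perfect, because the higher-scoring stratum sits further above the cut-off. At OR 2.0 the event rates are 0.57 and 0.43, so observed risk above the cut-off is 0.57×0.95/(0.57×0.95 + 0.43×0.80) = 0.61 against 0.43×0.83/(0.43×0.83 + 0.57×0.55) = 0.53.
2. Keep stratified sensitivity, specificity and likelihood ratios as a description of classification errors by stratum, and state that differences at a common cut-off are expected if age or sex is scored.
3. Optionally report score-by-sex and score-by-age interaction estimates with 95% confidence intervals as supportive only.

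Cost: wording and a little more analysis on data already planned. The limitation is precision. For a true score slope of 1 (score SD 0.9, sex OR 2, about 50% events), the 95% half-width of the score-by-sex interaction is about 0.66 at N = 300 and 1.2 at N = 100. The text should say that a null interaction is not evidence of equal performance.
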